## ***2.2. Primary Hypotheses***

Our main hypothesis is that an intervention designed to motivate and facilitate health care professionals' development through the implementation and maintenance of simple evidence-based guidelines can increase the use of evidence-based practices by birth attendants at the hospital level in Argentina and Uruguay.

The main specific aim of this project is to perform a randomized controlled trial of a behavioral intervention intended to increase the use of two evidence-based birth practices, the selective use of episiotomies and active management of the third stage of labor (injection 10 IU of oxytocin). We will randomize 24 hospitals in Department of Montevideo, Uruguay, the Province of Buenos Aires, Argentina, and the City of Rosario, Argentina.

The *main research questions* to test the main hypothesis are the following:

- Does the proposed intervention decrease the frequency of episiotomies (primary outcome) and of perineal sutures (secondary outcome) in the intervention hospitals relative to the control hospitals?
- Does the proposed intervention increase the frequency of injections of oxytocin during the third stage of labor (primary outcome), and decrease the frequency of postpartum hemorrhages (secondary outcome) in the intervention hospitals relative to the control hospitals?

*Secondary research questions* are the following:

- Does the proposed intervention increase the readiness to change of birth attendants (secondary outcome) in the intervention hospitals relative to the control hospitals?
- Are the effects, if any, sustained 1 year after the end of the intervention?

Our *other aims* are to do the following:

Facilitate capacity building within the Latin American Center for Perinatology (CLAP: Centro Latinoamericano de Perinatología) and among its network of hospitals, so that they may increase their ability to perform studies integrating behavioral and clinical research methods, and to perform large scale studies using state-of-the-art information technology.

Contribute to the Global Network by increasing access to a large number of Latin American hospitals that have the capacity to participate in multicentric randomized controlled trials and other clinical studies.

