### *5.1. Description of Questionnaires*

#### *5.1.1. Clinical data collection instruments*

Although the hospital will be the unit of analysis, we will collect patient data in order to obtain high quality data. We will collect data on primary and secondary outcomes and on potential confounders or effect modifiers. We will also collect data for safety monitoring (neonatal morbidity and mortality and maternal mortality). For clinical data there are 4 data collection forms (see appendix 6). CLIN1 form will collect data at the time of delivery, and ALTA1 will collect data on events from delivery to postpartum discharge. CLIN1 and ALTA1 forms will be used at data collection periods I and III. CLIN2 and ALTA2 will be used in data collection period II and IV (see figure 1 and section 5.2). The only difference between these two sets of forms is that CLIN1 and ALTA1 collect data on post-partum blood loss, while CLIN2 and ALTA2 do not.

All the hospitals in the project use a standard perinatal clinical history form (PIS form). This form registers the data of the obstetric history, prenatal care, labor, delivery, and neonatal outcomes. The additional information is recorded in other instruments and varies according to the hospital (i.e. laboratory results, ultrasound, etc.). This form was developed by CLAP in 1984 as a part of technical cooperation provided by the Centre to the countries in Latin America and the Caribbean. Some, but not all of the hospitals in the study enter the data in this document format using a computer program that was also developed by CLAP.

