### ***10.1. Analysis Plan***

Inference will be primary directed at the cluster (hospital) level. All analyses addressing the study research questions will use the “intention to treat” principle, thus comparing the original intervention group to the original nonintervention group, even if hospitals have withdrawn or shifted to another group. The data will be analyzed in collaboration by CLAP, UNC-CH, and the Global Network Data Center.

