#### ***10.5. Analysis of Primary and Secondary Hypotheses***

At the group level, the primary outcome variable is the percentage of primary and secondary outcomes during the three months following the end of the intervention. Despite having only 12 observations in each arm, since each percentage is based on a large number of births, one can use the Normal approximation to the Binomial distribution, and thus the individual percentages can be assumed to be Normally distributed. This implies that when evaluating the efficacy of the intervention using the mean percentages at the end of the intervention period, the Student's t-test is appropriate and its use is justified. Baseline frequencies will also be presented, and baseline to follow-up ratios will be computed. Mantel Haenszel summary risk ratios combining the individual ratios for each hospital in the intervention group and non-intervention group will be computed. The intervention and non-intervention groups will then be compared at the group level using Student's t-test on the logarithms of the summary risk ratio (Wyatt et al., 1998).

In addition, the data collected at the individual level will be used to explore the potential for confounding of the main effects of the intervention due to imbalances arising from the group randomization. Such multi-level analyses will use mixed model techniques (Littell et al., 1996), also known as hierarchical linear models (Bryk and Raudenbush, 1992). These models account for the clustering effect and the intra-hospital correlation of the women from a given hospital. Furthermore, we will use descriptive statistics and GEE modeling (Diggle et al., 1994) to study the evolution of frequencies of outcomes between the four data collection periods.

For the analysis of provider's "readiness to change", the analysis will include three variables, one assessing "readiness to change" episiotomy, one assessing "readiness to change" management of third stage of labor and one assessing attitude toward changing practice in general. Ordinal scales will be used for the responses. Data will be summarized in terms of medians and interquartile ranges. Non-parametric statistics will be used to compare the pre- and post-intervention differences between the control and intervention groups."

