### ***14.1. Description of Participants***

Birth attendants from 24 hospitals will be the subjects of this research. We expect the number of birth attendants to vary between 10 and 30 per hospital. They will be MDs, midwives, nurses, or other health professionals. Birth attendants will all be age 18 or older. There will be no exclusion based on sex, minority status, or other criteria.

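### Section 10.5 sets a non-parametric comparison of provider readiness scores with no hospital-level summary or cluster adjustment; a rank test on pooled providers would exceed its 5% level

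*Protocol*

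**What the plan says.** Readiness to change is a listed secondary outcome (sections 2.4.2 and 5.5.2.2) with its own research question in section 2.2: "Does the proposed intervention increase the readiness to change of birth attendants (secondary outcome) in the intervention hospitals relative to the control hospitals". Under section 5.3.2 every birth attendant in the participating hospitals answers the questionnaire twice, before randomisation and after the intervention ends. On cluster size, section 14.1 states: "We expect the number of birth attendants to vary between 10 and 30 per hospital".

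The analysis is in the last paragraph of section 10.5. It names three variables: episiotomy, third stage of labour, and changing practice in general. On how they are measured it says: "Ordinal scales will be used for the responses". The description of the scores comes next, with no mention of whether it is by provider or by hospital: "Data will be summarized in terms of medians and interquartile ranges". The paragraph closes with the comparison of the arms: "Non-parametric statistics will be used to compare the pre- and post-intervention differences between the control and intervention groups". It gives no named test, no unit of analysis and no method for clustering.

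The two paragraphs before it do settle the level. Clinical outcomes become one percentage per hospital, 12 per arm, compared by Student's t-test. For individual-level data on women the protocol specifies mixed models and adds: "These models account for the clustering effect and the intra-hospital correlation of the women from a given hospital". The general rule is in section 10.1: "Inference will be primary directed at the cluster (hospital) level".

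**The concern.** Hospitals are randomised, and providers are nested within them. An ordinary rank test assumes independent observations. Applied to pooled providers, it would treat some 240 to 720 attendants (24 × 10 to 24 × 30) as that many independent units when only 24 were allocated.

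The protocol's own theory makes independence implausible. Section 1.2.2 describes change spreading through the members of a social system. Each intervention hospital has its own opinion-leader team (section 4.3.2.2.2) and its own guidelines (section 4.3.2.2.5). Colleagues in one hospital should therefore tend to move together.

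At stake is a false claim that the intervention raised readiness, tested on three variables, for a secondary outcome with its own research question.

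**Working it through.** **The plan's own figures.** The protocol gives no sample size, power or correlation for readiness. Its clinical figures are computed at hospital level and reproduce. For episiotomy 40% to 20% with SD 15 points, two-sided 0.05 and 80% power:

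n per arm = 2 × (1.960 + 0.842)² × (15/20)² = 2 × 7.85 × 0.5625 = 8.8, so 9 per arm and 18 hospitals, as stated (power 0.807 at 9 per arm). The design is consistently hospital-level until the readiness paragraph.

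**Inputs for the check.**
- Providers per hospital, m: 10 to 30 (section 14.1).
- Hospitals per arm: 12 (section 2.1.1), or 9 if exclusions reduce the trial to the calculated size (section 10.3).
- Significance level: 0.05 (section 10.3), taken as two-sided because that reproduces the stated figures.
- Intra-hospital correlation (ICC) of the change scores: not in the protocol; assumed from 0.01 to 0.20.

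**Formula.** Clustering multiplies the variance of the arm comparison by the design effect DE = 1 + (m − 1) × ICC. A test that ignores this compares a statistic whose standard deviation is √DE with limits set for a standard deviation of 1. Its true type I error is therefore 2 × [1 − Φ(1.96/√DE)].

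**Worked case, m = 20, ICC = 0.05.** DE = 1 + 19 × 0.05 = 1.95; √1.95 = 1.396; 1.96/1.396 = 1.404; type I error = 2 × [1 − Φ(1.404)] = 16.0%.

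| Assumed ICC | m = 10 | m = 20 | m = 30 |
|---|---|---|---|
| 0.01 | 6.0% | 7.2% | 8.4% |
| 0.05 | 10.4% | 16.0% | 21.1% |
| 0.10 | 15.5% | 25.0% | 32.1% |
| 0.20 | 24.1% | 37.1% | 45.2% |

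**Check by simulation.** The setting was no true effect, ordinal change scores, 10 to 30 providers per hospital and 4,000 trials per cell. The Mann-Whitney (Wilcoxon rank-sum) test was applied once to pooled providers and once to the mean change score of each hospital.

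| Assumed ICC | Pooled, 12 per arm | Hospital means, 12 per arm | Pooled, 9 per arm | Hospital means, 9 per arm |
|---|---|---|---|---|
| 0 | 5.1% | 4.1% | 4.4% | 3.3% |
| 0.01 | 6.9% | 3.9% | 7.1% | 4.0% |
| 0.05 | 15.5% | 4.5% | 15.4% | 3.8% |
| 0.10 | 25.1% | 4.7% | 25.6% | 3.9% |
| 0.20 | 36.2% | 4.0% | 36.6% | 3.7% |

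The simulated pooled rates agree with the formula at m = 20. The hospital-level test stays below 5% throughout.

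**The case against.** The strongest reply is that the protocol never says provider responses will be treated as independent. The paragraph names no test, and a rank test on one summary per hospital is also non-parametric. Section 10.1 states a general hospital-level rule and then speaks of all analyses that address the research questions. Readiness is one of those questions and is worded as hospitals against hospitals. Section 5.1.1 adds: "Although the hospital will be the unit of analysis, we will collect patient data in order to obtain high quality data". On this view the paragraph is merely silent under a correct rule, and the test can be left to a SAP.

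Part of this stands. A reader might infer that the protocol prescribes an analysis with a type I error well above 5%. The documents do not support that: it follows only if providers are pooled and the ICC is not close to zero. The relevant ICC is that of change scores, from which stable hospital differences have been subtracted, so it may be small; at 0.01 the excess is modest. A reader might also infer that a false readiness result would be used to explain the clinical results. Nothing in the protocol says so, and section 5.6 gives the task of explaining a null effect to the process measures.

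The rest does not dispose of the point. Section 10.1 says only that inference is primarily at hospital level, and section 10.5 itself adds individual-level analyses. The sentence in section 5.1.1 concerns patient data in the clinical forms. The mixed models in section 10.5 are tied to the women. The readiness paragraph moves from ordinal responses to medians to non-parametric tests, which reads as rank methods chosen because individual responses are ordinal. Having fixed the variables, summaries, contrast and class of test, it leaves out the one element that decides validity in a cluster trial, which its neighbouring paragraphs supply.

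**Conclusion.** The point holds in conditional form. Section 10.5 specifies the readiness comparison without a hospital-level summary or cluster adjustment. That is unlike the clinical outcomes in the same section and out of line with section 10.1. If carried out as it most naturally reads, a nominal two-sided 5% rank test would have a type I error of about 6-8% at ICC 0.01, 10-21% at 0.05 and 16-32% at 0.10, across 10 to 30 providers per hospital. These rates are per test, for each of three variables.

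The direction is certain for any positive ICC under pooling. The size rests on assumed ICCs, and the formula treats hospitals as equal in size. The primary outcomes, which are analysed as hospital percentages, are not affected.

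**What to change.** Replace the last sentence of the readiness paragraph in section 10.5. For each of the three readiness variables, compute one change summary per hospital: the mean or median score after the intervention minus the mean or median before, with the choice named in advance. Compare the arms across hospitals with a Wilcoxon rank-sum test. State that provider-level medians and interquartile ranges are descriptive only. The simulated error rates above were obtained with the mean.

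This needs no extra data or visits. A difference between the two hospital-level scores also does not require linking each provider's two questionnaires. The price is larger p-values and less apparent power for this secondary outcome, because the comparison rests on at most 12 against 12 hospitals.

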#### 5.3.2. Questionnaires to birth attendants

Questionnaires will be administered to all birth attendants in the participating hospitals prior to randomization (immediately after Period I) and after the end of the intervention (immediately after Period III).

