#### 5.5.2.2. Other secondary outcome

Provider's readiness to change with respect to episiotomies and management of third stage of labor.

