### ***10.3. Sample Size***

A preliminary analysis of 1995-98 PIS data from 22 Argentinean hospitals showed a baseline frequency of episiotomies among vaginal deliveries of 42%, with a standard deviation of 11%. To protect against changes in the standard deviation (Lomas et al., 1991), we have based our sample size calculations on a standard deviation of 15%. Thus, we will need 18 hospitals (9 intervention and 9 control) to identify a decrease of episiotomy rates from 40% to 20%, with a 0.05 significance level and a 80% power. Our previous analyses of PIS data have shown that about 25% of deliveries are among primiparae, and 75% among multiparae. A reduction of the general episiotomy rate from 40% to 20% could be achieved by reducing the rate among primiparae from 80% to 40%, and the rate among multiparae from 26% to 13%. The rates after the intervention would be similar to the rates achieved in a previous trial (Argentine Episiotomy Trial Collaboration Group, 1993) and are thus potentially attainable. However, the sample size of 18 hospitals will allow us to identify a smaller decrease of episiotomy rates among primiparae vaginal deliveries, from 80% to 60%, with a 0.05 significance level and a 80% power. Assuming a baseline frequency of perineal sutures among primiparae of 85% with a standard deviation of 15%, our sample size of 18 hospitals will give us a power of 80% to identify a reduction of frequency of perineal sutures to 65%, with a 0.05 significance level.

We expect the use of oxytocin during the third stage of labor to increase from 10% to 50%. However, our sample size will allow us to detect smaller changes. Assuming a baseline frequency of injections of oxytocin of 10% and a standard deviation of 5%, the sample size of 18 hospitals will give us a power higher than 95% to identify an increase of use of oxytocin from 10% to 20%, with a 0.05 significance level. Assuming a baseline PPH incidence rate of 15% and a standard deviation of 5%, the sample size of 18 hospitals will give us a power of

84% to identify a reduction from 15% to 8%, and a power of 56% if the reduction were from 15% to 10%.

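### Readiness to change is compared as pre/post differences; adjusting for the baseline survey would be at least as powerful, by an amount that depends on correlations the protocol does not give

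*Protocol*

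**What the plan says.** Sections 2.4.2 and 5.5.2.2 of the Protocol list one non-clinical secondary outcome: "Provider's readiness to change with respect to episiotomies and management of third stage of labor". It answers a secondary research question in section 2.2.

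On timing, section 5.3.2 states: "Questionnaires will be administered to all birth attendants in the participating hospitals prior to randomization". A second round follows Period III. Section 5.2 sets the data collection periods one year apart, so the two surveys are about two years apart. On numbers, section 14.1 states: "We expect the number of birth attendants to vary between 10 and 30 per hospital".

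Section 10.5 defines three readiness variables, each scored on an ordinal scale. The comparison between arms is stated as: "Non-parametric statistics will be used to compare the pre- and post-intervention differences between the control and intervention groups". No test is named, and nothing says whether the difference is taken per attendant or per hospital. The descriptive summary is a separate statement: "Data will be summarized in terms of medians and interquartile ranges". Section 10.1 directs inference primarily at the hospital.

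**The concern.** The natural reading of 10.5 is a change score, follow-up minus baseline, compared between arms by a rank method. That subtracts the baseline in full, however well or badly it predicts follow-up. When prediction is weak, subtraction adds the baseline's noise to the outcome. A baseline-adjusted comparison weights the baseline by its observed relation to follow-up.

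Several features could make prediction weak here: the surveys are about two years apart, each hospital contributes only 10 to 30 attendants, and no linking of a person's two answers is described. Subtracting ordinal codes also treats the steps as equal, which sits awkwardly with a rank-based plan. At stake is the chance of detecting a real change in readiness with at most 24 clusters.

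**Working it through.** **The plan's own figures.** There is none for readiness. Section 10.3 plans for episiotomy, "to identify a decrease of episiotomy rates from 40% to 20%, with a 0.05 significance level and a 80% power", with an SD of 15%. The usual formula reproduces its size: n per arm = 2 × (1.960 + 0.842)² × 15² / 20² = 8.83, so 9 per arm or 18 hospitals (power 80.7%). This does not bear on readiness.

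**Variance.** Let s² be the common variance of the hospital score at each survey and rho the correlation between the two observed scores.

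- Change score: 2s²(1 − rho)
- Baseline-adjusted: s²(1 − rho²)
- Follow-up only: s²
- Change over adjusted: 2(1 − rho) / [(1 − rho)(1 + rho)] = 2/(1 + rho)

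The ratio exceeds 1 for every rho below 1. The change score beats follow-up alone only when 2(1 − rho) < 1, that is rho > 0.5.

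**Power.** Suppose the adjusted analysis has 80% power at two-sided 0.05. The change score then has power Φ(2.802 × √[(1 + rho)/2] − 1.960).

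| rho | variance ratio | change-score power | loss (points) |
|---|---|---|---|
| 0 | 2.00 | 50.8% | 29 |
| 0.3 | 1.54 | 61.7% | 18 |
| 0.5 | 1.33 | 67.9% | 12 |
| 0.6 | 1.25 | 70.7% | 9 |
| 0.8 | 1.11 | 75.7% | 4 |
| 0.9 | 1.05 | 78.0% | 2 |

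**From hospital correlation to observed rho.** With different respondents at the two surveys, sampling noise lowers rho by roughly the factor ICC / (ICC + (1 − ICC)/m). At m = 20 this is 0.1/(0.1 + 0.045) = 0.69 for ICC 0.1 and 0.2/(0.2 + 0.04) = 0.83 for ICC 0.2. A hospital-level correlation of 0.3 to 0.6 thus becomes about 0.21 (0.3 × 0.69) to 0.50 (0.6 × 0.83), and slightly less after scoring on five levels.

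**Simulation.** From the Protocol: 12 hospitals per arm and 10 to 30 attendants. Assumed: five levels, a latent shift of 0.5 SD, ICC 0.1 or 0.2, and, where the same attendants answer twice, a within-attendant correlation of 0.5. Each cell gives power for the rank test on differences of hospital means / rank ANCOVA on hospital means, then the loss in points (3000 simulations per setting).

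| Hospital correlation | Unlinked, ICC 0.1 | Unlinked, ICC 0.2 | Same attendants, ICC 0.1 | Same attendants, ICC 0.2 |
|---|---|---|---|---|
| 0.3 | 59/82: 23 | 43/63: 20 | 68/85: 17 | 47/66: 19 |
| 0.6 | 72/85: 13 | 58/71: 13 | 84/91: 7 | 65/75: 10 |
| 0.8 | 82/89: 7 | 74/81: 7 | 94/96: 2 | 84/87: 3 |

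A separate run of the same model gave losses of about 10 to 23 points (unlinked, 0.3 to 0.6), 5 to 16 (same attendants, 0.3 to 0.6) and 1 to 9 (0.8). The ends of the ranges move by about three points between runs. Type I error was 4 to 6% in the null settings run.

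**The case against.** The planned comparison is valid, and 10.5 leaves the exact test and the unit open, which a statistical analysis plan may settle. Readiness is the last-listed secondary outcome, has no power claim in 10.3 and touches neither primary outcome. Section 5.3.2 surveys all attendants both times, so many may answer twice, and a stable hospital culture could make the correlation high. The loss is then a few points. All of this stands and limits the point to an efficiency gain. It does not remove the point, because 10.5 does fix the contrast as a pre/post difference.

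Three stronger readings are tempting and are not supported.

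- **That the plan costs 17 to 26 points.** A figure of that size comes from testing differences of hospital medians. Section 10.5 gives medians and interquartile ranges as a summary and does not make them the test input. In the closed-form calculation, a loss of that size at 80% adjusted power needs an observed rho of about 0.34 down to 0.08, and the Protocol states no correlation.
- **That the baseline survey is wasted.** A change score uses it, and beats follow-up alone once the observed rho exceeds 0.5. At rho 0.7, when the adjusted analysis has 80% power, the figures are 73% against 52%.
- **That the test gives false positives.** The simulated type I error shows no sign of this when the hospital is the unit.

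**Conclusion.** The point holds as a modest one about efficiency. On the natural reading of 10.5, baseline adjustment is more efficient than the change score for any correlation below 1, and rank ANCOVA had the higher power in every simulated setting. The size is conditional: about 10 to 23 points of power at a hospital-level correlation of 0.3 to 0.6 with unlinked respondents, about 5 to 16 if the same attendants answer twice, and about 1 to 9 at 0.8. These rest on the assumed five levels, 0.5 SD shift, ICC of 0.1 to 0.2 and within-attendant correlation of 0.5. Only the number of hospitals and the number of attendants come from the Protocol. No stated figure is wrong and the primary outcomes are unaffected.

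**What to change.** In section 10.5, replace the comparison of pre/post differences by a comparison of the hospital summary score after Period III, adjusted for the same hospital summary after Period I. Take the hospital as the unit, in line with 10.1. Rank ANCOVA on hospital mean scores keeps the analysis non-parametric. It needs no linking of individual answers. A hospital mean does treat the scale steps as equal, as a change score also does. Keep medians and interquartile ranges for description. Define the summary from the actual response scale: the questionnaire sits in Appendix 6, which is not in the document, so the wording should not presuppose stage-of-change categories.

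The cost is a sentence in the Protocol or the statistical analysis plan, settled before follow-up data are seen. No new data are needed.
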